#### 9.6 FOLLOW-UP SAFETY CONTACT

The site will contact the participant approximately 7 days (range 7-10) after her last visit. She will be asked about any AEs experienced and medications taken since her last visit. In addition, she will be asked if her partner has had any AEs involving the urogenital system or associated with the use of the product, and whether he has had any serious adverse events. The participant will then be exited from the study, unless she has symptoms requiring follow-up.

#### 9.7 UNSCHEDULED VISITS

Unscheduled visits may be performed at the participant's request or as deemed necessary by the investigator at any time during the study.

When an unscheduled visit occurs in response to an AE experienced by a study participant, study staff will assess the reported event clinically and provide or refer the participant to appropriate medical care, as necessary. Unscheduled visits that require examination or interview due to symptoms will be recorded in eCRFs.

All AEs will be evaluated and follow-up of any observed abnormalities will proceed according to Section 13.

#### 9.8 DISCONTINUATION PROCEDURES

If a participant discontinues early from the study, she will be asked if she has had any new or worsening medical problems or symptoms or used any medication since the last study visit. In addition, she will be asked if her partner has had any AEs involving the urogenital system or associated with the use of the product (as applicable), and whether he has had any serious adverse events.

If it has been less than 7 days since the participant's last use of study product(s), then she will be contacted for additional follow-up safety information 7 days (range 7-10) days after her last product use, after which she will be exited from the study unless she has symptoms requiring follow-up (**Section 1.1**). If, at the time of early discontinuation, it has been more than 7 days since the participant's last study product use, she will be exited from the study at the time of discontinuation.

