Safety data are also needed. Treatment-emergent systemic and genital adverse events (AEs) will be collected from both the female participants and their male partners, via report from the female participants. Additional information on systemic effects in the female participant will be collected in the form of standard safety labs (complete blood count and serum chemistries) as well as labs that are specific to Ovaprene™. The latter will include serum ferritin, a protein that is involved in iron storage and which becomes elevated in situations of iron overload. While the likelihood of iron overload developing from the small amount of iron in Ovaprene™ (569.8 mg, ¹ the maximum amount that could be released over an entire cycle of use, as compared with 325 mg daily included in many multivitamins) is minimal, systemic safety will be documented.

Additional genital safety data will come from findings via pelvic exam, including colposcopy, and changes in Nugent score and microflora. The ability of the product to maintain vaginal innate immunity will be assessed using antibacterial activity in the CVF and soluble markers of inflammation in CVF. Any potential colonization of the product by *Staphylococcus aureus* or group A Streptococcus, the organisms associated with Toxic Shock Syndrome, will be assessed on devices that have been worn over a cycle of use.

Finally, a product that is unacceptable to women or their partners will not have commercial potential. This study will collect acceptability information from both partners. It will also assess the proportion of women for whom Ovaprene™ will fit and those who can insert, position, and remove the device with only written instructions. It will also determine where, in relation to the cervix, the device comes to reside after insertion and after sex, and the relationship of that location to PCT results, safety, and acceptability. The study described here will have as its objectives the collection of all these types of data − changes in PCT results due to device use, release, safety, acceptability, and fit.

Version: 06.00 (FINAL) Date: June 13, 2019

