#### 7.3 NUMBER OF SUBJECTS

Approximately 45 women will be enrolled with the goal to have approximately 25 participants complete the trial. Subjects who discontinue early may be replaced.

Version: 06.00 (FINAL) Date: June 13, 2019

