# e) Visit OS5, 21-23 days after insertion (approximately cycle day 27-29, or sooner if menses is expected to begin):

- An acceptability questionnaire will be administered.
- Blood will be drawn for CBC, serum chemistries, and serum ferritin.
- The procedures described above for Visit OS2 will be completed, except that no OPK will be dispensed.
- Ovaprene™ will be removed and stored for later analysis.
- A colposcopic exam will be completed.
- Cervical mucus will be collected for ferrous gluconate and pH.
- The participant will next undergo an Ovaprene™ PCT cycle. She will be instructed to:
  - o Call at the onset of her next menses to tentatively schedule Visit OP1 on the day following the end of menses. Adjustments to this visit will be made as needed.
  - Use non-spermicidal, lubricated condoms (dispense as needed at this visit) from the first day of her next menses until day 10 of that cycle, and to abstain from intercourse and other vaginal activityr starting on Day 10 until after Visit OP2, the CMC visit.

<sup>q Assaying for ferrous gluconate in the cervical mucus is considered exploratory throughout the study.

"Other vaginal activity" includes insertion of vaginal medications/products other than the study product (prescription or over-the-counter), as well as insertion of sex toys, fingers, or anything else into the vagina. Tampons may be used during all days of menses in the Baseline PCT and Caya PCT cycles, but only during the first three days of menses in Ovaprene cycles.

Version: 06.00 (FINAL) Date: June 13, 2019

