#### 3.1.3 Analysis Conventions

This section details general policies used for the statistical analyses. Departures from these general policies may be given in the specific detailed sections of this statistical analysis plan. When this situation occurs, the rules set forth in the specific section take precedence over the general policies. The following policies will be applied to all data presentations and analyses.

- Discrete variables' summary statistics will consist of the number and percent of responses in each category
- Continuous variables' summary statistics will include the sample size (number of non-missing observations), mean, median, standard deviation (SD), minimum and maximum, abbreviated as "6-number summary statistics", where minimum and maximum may be replaced with 25th and 75th percentiles, i.e., interquartile range (IQR), if desired.
- All mean values will be formatted to one more decimal place than the measured value. Standard deviation values will be formatted to two more decimal places than the measured value. Median values will be formatted to same decimal place as the measured values when that is possible without losing accuracy; otherwise, they will be formatted to one more decimal place than the measured values.
- All percentages will be rounded to one decimal place. The number and percent of responses
  will be presented in the form XX (XX.X), where the percentage is in the parentheses. The
  decimal of the percentage may be dropped due to space constraints when creating a table.
  The denominator for percentage calculations will be the number of non-missing observations,
  or the analysis population's sample size if no such number of non-missing observations is
  presented along with the categorical values.
- All by-subject data listings will be sorted for presentation in order of site number, subject number, and date of procedure or event.
- When necessary for analysis purposes, partial dates will be completed (i.e., turned into complete dates) using the most conservative approach: for example, if a concomitant medication start date had Month and Year parts only, it's assumed to be the first day of that month; while if the stop date had Month and Year parts only, it's assumed to be the last day of that month.
- All analysis and summary tables will have the population sample size in the column heading.
- Calculating change from Baseline to a visit will be done as follows:

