#### 3.8 Acceptability Questionnaire

An acceptability questionnaire developed for this study is administered at the Ovaprene® cycles. The following questions' answers will be summarized with the number and percent of subjects in each response category at each visit, as well as shift tables (frequencies of each categorical response at one visit cross tabulate with the frequencies from another visit, from Visit OS5 to Visits OP3A and OP3B, and from Visit OP3A to Visit OP3B):

- 1. How would you describe the ease of Ovaprene® insertion? (Response: Very easy, Fairly easy, Neither easy nor difficult, Somewhat difficult, Very difficult)
- 2. During the study, were you aware of the Ovaprene® device during your normal daily activities? (Response: Always, Most of the time, Some of the time, Rarely, Never)
- 3. How did it feel to have the Ovaprene® device in place when you were not having sex? (Response: Usually comfortable, Neither comfortable nor uncomfortable, Sometimes comfortable and sometimes uncomfortable, Usually uncomfortable)
- 4. Have you had sex with the device in place? (Response: No, Yes)
- 5. How did it feel to have the Ovaprene® device in place when you were having sex? (Response: Usually comfortable, Neither comfortable nor uncomfortable, Sometimes comfortable and sometimes uncomfortable, Usually uncomfortable)
- 6. If Ovaprene® became available and you needed protection from pregnancy, would discomfort prevent you from using it? (Response: No, Yes)

- 7. Was your partner aware of the device when you were having sex? (Response: Always, Most of the time, Some of the time, Rarely, Never)
- 8. Did your partner experience discomfort from the device when you user having sex? (Response: Always, Most of the time, Some of the time, Rarely, Never)
- 9. If Ovaprene® became available and you needed protection from pregnancy, would your partner's discomfort prevent you from using it? (Response: No, Yes)
- 10. Do you think it would be possible for a woman to use this product without her partner's knowledge? (Response: No, Yes)
- 11. While you have already had tubal sterilization, if you needed protection against pregnancy, how likely would you be to use Ovaprene® if it became available? (Response: Very unlikely, Unlikely, Likely, Very likely)
- 12. Have you ever used a diaphragm when you needed protection against pregnancy? (Response: No, Yes)

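### By-visit acceptability percentages may be biased upward, because women who stop Ovaprene early are not given the questionnaire when they leave

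*Protocol*

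**What the plan says.** **When the questionnaire is given.** For visit OS5, at the end of the first Ovaprene cycle, Protocol 9.4.1 states: "An acceptability questionnaire will be administered". Protocol 9.5.1 schedules it again at OP3 in each of the two PCT cycles. In Protocol Appendix 1 and SAP 4.1 the questionnaire row is marked at these visits only, and the unscheduled-visit column is blank.

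**What is asked at early exit.** Protocol 9.8: "If a participant discontinues early from the study, she will be asked if she has had any new or worsening medical problems". The sentence goes on to symptoms and medication, and the next covers partner adverse events. The questionnaire is not mentioned.

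**How answers are tabulated.** Under SAP 3.8 the closed questions are "summarized with the number and percent of subjects in each response category at each visit", with shift tables between pairs of visits. SAP 3.1.3 gives the default: "The denominator for percentage calculations will be the number of non-missing observations". The population size is the fallback where no count of non-missing observations is shown. No handling of missing questionnaires is specified.

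**How many may be lost.** Protocol 7.3: "Approximately 45 women will be enrolled with the goal to have approximately 25 participants complete the trial". It adds: "Subjects who discontinue early may be replaced".

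**Why acceptability is collected.** The Protocol introduction says that "a product that is unacceptable to women or their partners will not have commercial potential".

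**The concern.** Women who find the device uncomfortable or troublesome are plausibly more likely to leave. If leavers are not asked for ratings and each percentage is taken over those who answered, the tables describe women who tolerated the device long enough to reach the visit. Replacement of early stoppers can refill the tables with women who stayed. The likely result is an upward bias in the ratings of comfort, likelihood of use and likelihood of recommending.

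The stake is the reading of a tertiary objective to which the protocol itself attaches commercial weight. No success threshold or test rests on these percentages: Protocol 14.2.5 plans a qualitative evaluation only.

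**Working it through.** The plan contains no calculation for acceptability to reproduce. Protocol 14.1 says the study size was set on feasibility. The check is therefore in two parts.

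**1. Who is missing from which table**

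| Time of stopping | Questionnaire data available |
|---|---|
| Before OS5 | None |
| After OS5, before the first OP3 | OS5 only; little or nothing on sex or partner discomfort, because the safety cycle has no intercourse |
| After the first OP3, before the second | OS5 and first OP3; absent from the second OP3 and its shift tables |

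Only the first group is wholly unrated.

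**2. How far a by-visit percentage could differ from the all-user figure**

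Inputs from Protocol 7.3: about 45 enrolled and 25 completing. Implied non-completion is (45 − 25)/45 = 20/45 = 44.4%. This is a ceiling for Ovaprene users lost, because enrolment comes before the Caya cycle and some women will leave without using Ovaprene. The documents do not give the number of users lost.

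Assumption, not from the documents: 25 women answer at the last questionnaire and 20 of them are favourable. The by-visit figure is 20/25 = 80.0%, with an exact (Clopper-Pearson) 95% interval of 59.3% to 93.2%.

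Let m be the Ovaprene users with no answer at that visit.

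- Lower bound, all m unfavourable: 20/(25 + m)
- Upper bound, all m favourable: (20 + m)/(25 + m)
- Intermediate case, m half as favourable as responders: (20 + 0.4m)/(25 + m)

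| m | Lower bound | Half as favourable | Upper bound |
|---|---|---|---|
| 5 | 20/30 = 66.7% | 22/30 = 73.3% | 25/30 = 83.3% |
| 10 | 20/35 = 57.1% | 24/35 = 68.6% | 30/35 = 85.7% |
| 20 (ceiling) | 20/45 = 44.4% | 28/45 = 62.2% | 40/45 = 88.9% |

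The bounds run both ways, but there is more room below 80.0% than above it: at m = 5, 13.3 points below against 3.3 above.

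The SAP's choice of denominator also matters. With m = 5 the same data would print as 20/25 = 80.0% under the default rule, or 20/30 = 66.7% if the fallback to population size applied. SAP 3.8 does not say which holds for these tables.

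**The case against.** Much is collected on early stoppers outside the exit contact.

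- **They are not all unasked.** A woman who stops after OS5 has already rated insertion, awareness, comfort without sex, likelihood of use and likelihood of recommending, and she is in the OS5 table.
- **Dislodgement and device problems are recorded elsewhere.** The diary prompts for device problems throughout (Protocol 9.1.2). SAP 3.9 g and h summarise diary expulsions, partial displacements and clinician-assessed position for each woman.
- **Physical discomfort is asked about at exit.** Protocol 9.8 covers symptoms, and Protocol 13.3 lists genital pain and irritation among expected adverse events. Reasons for stopping are tabulated (SAP 3.2), and adverse events leading to discontinuation are listed (SAP 3.7.1).
- **The fall in numbers would be visible.** SAP 3.1.3 puts the population size in every column heading, and the visits are tabulated separately.
- **Questions on sex could not be answered earlier in most cases.** Intercourse is barred in the safety cycle. Before the postcoital act in a PCT cycle, only sex with condoms before day 10 is allowed.

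All of this stands, and it rules out the stronger reading that a reader might infer: that women who quit over discomfort or dislodgement vanish from the data and that acceptability is therefore overstated. The documents show neither.

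What remains is narrower. None of these sources gives a leaver's own rating of willingness to use or recommend. The reasons in Protocol 7.5 have no category for discomfort or dislodgement short of an adverse event, so such a woman could be recorded simply as having withdrawn consent.

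**Conclusion.** The concern holds in limited form. If the plan is followed exactly, women who stop before OS5 give no acceptability ratings, later stoppers drop out of later tables, and percentages by default exclude them. This missingness may be related to the outcome, and upward bias is its plausible direction.

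The size cannot be stated from the documents. Under the assumed 20 of 25 favourable, five unanswered users put the all-user figure between 66.7% and 83.3%. That range lies inside the exact 95% interval of 59.3% to 93.2%, so at that level of loss sampling error is the larger uncertainty. With ten unanswered users the lower bound, 57.1%, falls just below the interval. The lower bounds take every non-responder as unfavourable and should not be read as estimates.

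Since the endpoint is tertiary and descriptive, this is a worthwhile low-cost improvement and not a threat to the study's main conclusions.

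**What to change.** 1. **Protocol 9.8 and both schedules of assessments.** Give the existing questionnaire at the discontinuation visit or contact to any woman who has used Ovaprene. Ask the questions on sex only if she has had sex with the device in place.
2. **SAP 3.8.** Keep the by-visit and shift tables. Add one supplementary display for questions that do not depend on sex, for example likelihood of use and of recommending. It should show each woman's last available response, the visit it came from, and all Ovaprene-treated women as the denominator. Early stops without a response should form a separate category, by reason.
3. **SAP 3.9 g.** Use that definition for the two end-of-study acceptability responses it calls for. At present no questionnaire is scheduled after OP3 of the second PCT cycle, so the term is undefined.

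The cost is a few minutes at a contact already required, plus one table. There are two drawbacks. Some women who leave will not answer, though the display will at least count them. The last responses will also come after different lengths of exposure, which is why the display should supplement the by-visit tables and leave out the questions on sex.

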#### 9.9 DATA COLLECTED FROM MALE PARTNERS

Data will be collected from male partners specific to AEs involving the urogenital system, adverse events associated with the use of the product, and all serious adverse events. Prior to each visit, the female participant should ask her partner if he has any AEs meeting these criteria; any AE information provided to the female participant should be communicated to the study coordinator at the participant's next clinic visit or phone call, whichever comes first. The study staff will contact the male partner for clarification of events, as needed. All AEs reported by the male and meeting the above criteria will be recorded on an AE eCRF and will be reported according to the procedures described in **Section 13**.

Male partners also will be instructed to contact the site if they experience severe urogenital symptoms or an SAE. The site will arrange for an evaluation at the center or a possible referral if necessary or desired by the male partner. Male partners will not be required to attend any other clinic visits.

Version: 06.00 (FINAL) Date: June 13, 2019

#### 10. TREATMENT OF PARTICIPANTS

# **10.1 STUDY PRODUCTS**

Table 12 Ovaprene™

	Product
Product Name:	Ovaprene™
Dosage Form:	Not applicable
Unit Dose	1 device
Route of Administration	Vaginal barrier method; placed intravaginally at the end of menses
	and left in place until the beginning of the next menses
Physical Description	Single-size contraceptive device.
Manufacturer	Manufactured by Poly-Med

#### 10.2 CONCOMITANT MEDICATIONS

Prohibited medications include use of intravaginal products at times specified in the protocol, as well as all hormonal contraceptives and treatment for BV and STIs. All concomitant medications will be recorded on CRFs.

# 10.3 TREATMENT COMPLIANCE

Treatment compliance will be evaluated by self-report. Menses, intercourse, use of intravaginal products, AEs, medications, and problems with the device will be recorded in the eDiary by the participant.

#### 10.4 BLINDING

This is an open label study, thus no product blinding is intended. Ovaprene™ will not be repackaged. Although the individual examining cervical mucus for midcycle characteristics and the presence of sperm and examining vaginal specimens for the presence of sperm is not typically blinded in studies of this type due to the logistical difficulties inherent in doing so, the individual performing these tasks at the EVMS site will be blinded as to the type of visit and use of a barrier, if any.

#### 10.5 RANDOMIZATION

This is an open label study, in which all participants will use the same study product, thus no randomization will take place.

Version: 06.00 (FINAL) Date: June 13, 2019

# 11. STUDY MATERIALS AND MANAGEMENT

#### 11.1 DESCRIPTION OF STUDY PRODUCT

Ovaprene™ is a new, prescription monthly method of birth control that combines a porous, soft mesh cervical barrier encircled by a silicone intravaginal ring that slowly releases non-hormonal ingredients that antagonize sperm motility and viability. The device is inserted at the end of menses, left in place over the course of one menstrual cycle, and removed at the start of menses. Ovaprene™ is designed as a single size device with a diameter of 55 mm, similar to FDA approved, hormone-containing 54 mm diameter NuvaRing® device, eliminating the need for a specifically sized fitting or insertion by a health care professional. Thus, Ovaprene™ is a single device designed to provide the features that contracepting women want: efficacy, ease of use, ease of adherence, low or no side effects and easy reversal.

Ovaprene™ was studied in a human clinical trial as a non-significant risk device published in 2009.¹ Prior to this study, Ovaprene™ underwent a series of *in vitro* and animal tests to determine usability and design parameters, and to assess its initial safety and contraceptive efficacy. These background data are considered proprietary, but major conclusions are summarized in this section, with additional detail published in Del Priore *et al.*¹

To determine the putative barrier properties of Ovaprene™, the effectiveness of the mesh component in blocking human sperm was tested in an *in vitro* environment having features similar to those of the human cervix. After 20 hours of continuous exposure to sperm, there was no evidence of sperm passage through the Ovaprene™ mesh. Burst testing, under forces two orders of magnitude higher than expected during normal use, confirmed that no delamination or slippage of the mesh component from the ring matrix is expected during placement, and up to 35 days of use.

Uniform mixing of the spermiostatic components throughout the silicone matrix is controlled during the ring manufacturing process. In an *in vitro* model simulating *in vivo* conditions, ferrous gluconate (FG) is released from the ring immersed in synthetic vaginal fluid in three different stages. These consist of an initial burst (day 1), erosion (days 2-7) and diffusion (days 5-35). Release studies evaluated the cumulative concentration of each component and demonstrated that the average concentration of FG throughout the testing period exceeded the minimal levels required for spermiostatic activity based on literature values.

Ovaprene™ already meets the necessary toxicology requirements for human studies and regulatory approval. Ovaprene™ has been found non-mutagenic and non-clastogenic via Gene Mutation testing, Chromosomal Aberration testing, and Rodent Bone Marrow Micronucleus Assay testing, and has met the International Standards Organization (ISO 10993-10 guidelines) requirements of the Kligman Maximization Test, Rabbit Pyrogen Test, and Intracutaneous Injection Test. A four-week Muscular Implantation test in rabbits demonstrated no difference compared to controls, and a Primary Vaginal Repeat Exposure test in rabbits demonstrated that the extracts of Ovaprene™ are non-irritating.

The Ovaprene™ ring was miniaturized to evaluate contraceptive activity in rabbits. The adapted device was 100% effective in preventing pregnancy in this model.

An open label, single-arm, observational study was conducted with Ovaprene™ in sexually active women.¹ Twenty women were enrolled. Baseline Pap tests, vaginal cultures and colposcopy were performed with follow-up post-coital testing and acceptability questionnaires. Participant questionnaires revealed no pain, bleeding, or discharge and no colposcopic abnormalities were observed. Semi-quantitative cultures yielded no significant changes in vaginal flora. Post-coital testing assessed preliminary contraceptive activity by assessing motile sperm in ten high powered fields. There were no normal, forward-moving sperm seen in the

Version: 06.00 (FINAL) Date: June 13, 2019

vaginal pool or cervical canal in any of the participants, consistent with high spermiostatic activity. A low pH was maintained throughout the duration of the study [of 28 measurements, 22 (79%) recorded a pH of 5.5 or less throughout the 28-day study] presumably through the release of ascorbic acid (AA) and polyglycolide (PG) from the Ovaprene™ ring.

Ovaprene™ was developed by Adva-Tec, Inc., a majority owned subsidiary of Poly-Med, Inc. Poly-Med holds twelve issued patents in the U.S. and three issued European patents pertinent to the invention and protection of Ovaprene™ technology. Since the completion of the pilot study summarized above, Poly-Med/Adva-Tec has sought a suitable commercialization partner and recently entered into an agreement with Daré Bioscience, a company committed to both advancing the clinical development of novel contraceptive products and creating comprehensive global strategies for the commercialization of these products. The principals of Daré Bioscience have an excellent track record of commercializing women's health products. With a commercialization strategy identified, Poly-Med is now positioned to continue the development of this innovative technology. These three world class companies have joined forces to complete the clinical development of Ovaprene™ and bring this important product to the marketplace.

[figure not shown]
The FDA has determined that the Center for Devices and Radiological Health (CDRH) will be the lead reviewing agency for Ovaprene™, and that it will be reviewed in the context of other barrier contraceptive devices using active agents, for which clearly defined clinical and regulatory pathways toward FDA clearance exist. This pathway includes the following three steps: (1) conducting standard biocompatibility, safety exposure, and toxicology studies; (2) obtaining safety and preliminary efficacy data in 20-30 human subjects [the objective of this study]; and (3) conducting a larger scale, single arm safety and efficacy study in at least 200 subjects, comparing its efficacy results to historical controls.

